8.2. Other Efficacy Endpoints

8.2.1. Subjective Assessment of Lens Handling

Individual CLUE handling items will be summarized using frequency tables of rating categories by treatment. The derived lens handling score at Visit 2 will be summarized using descriptive statistics by treatment arm.

8.2.2. Average Daily Wear Time (in Hours)

The average daily wear time and the comfortable wear time recorded at Visit 2 will be summarized at subject level by treatment arm.

8.2.3. Clinically Significant Slit-lamp Findings

Proportion of eyes with clinically significant (Grade 3 or 4) slit lamp findings overfitting and post-fit evaluations including unscheduled visits is a secondary endpoint and will be summarized by treatment arm.

8.2.4. Unacceptable Lens Fitting

Proportion of eyes with unacceptable fitting recorded at any evaluation performed on or after the first fitting is a secondary endpoint and will be summarized by treatment arm.

8.2.5. Reported Ocular Symptoms

Proportion of eyes with reported ocular symptoms at Visit 1, Visit 2 and any other unscheduled visit is a secondary endpoint and will be summarized by treatment arm.

9. Safety Analysis

Safety analysis will be conducted on safety population by treatment actually received by subjects.

9.1. Adverse Events

All adverse events will be coded using the MedDRA®. The version of the MedDRA will be indicated in the footnote of relevant AE tables based on the current version used in the clinical data. Number of subjects or eyes with adverse events and number of events will be tabulated by SOC and PT levels. Ocular and non-ocular adverse events will be summarized separately.

Ocular adverse events will be summarized at the eye level and at the subject level.

For eye level summaries, the individual eye will be considered as the unit of analysis. If multiple events occur in the same eye of the same subject, they will be counted only once for that eye.

For subject-level ocular adverse event summaries, the subject will be considered the unit of analysis. Therefore, if both of a subject's eyes report the same adverse event, the subject will be counted once in the numerator and denominator when calculating the percentage of subjects with that adverse event.

For non-ocular adverse events, the subject will be considered as the unit of analysis.

Treatment emergent adverse events (TEAE) are defined as those events that began on or after test lens insertion after randomization.

Significant non-ocular adverse events are non-serious TEAEs that led to temporary or permanent discontinuation of the test article.

Significant ocular adverse events are ocular adverse events with a significant diagnosis of any of the following:

- Contact Lens induced Peripheral Ulcer (CLPU)
- Significant Infiltrate Event (SIE)
- Superior Epithelial Arcuate Lesions (SEALS)
- Significant Elevation in IOP (Intraocular pressure)
- Argyrosis
- Pyogenic Granuloma
- Dacryocystitis
- Canaliculitis
- Other ocular AE reported as significant by the investigator

For the purpose of inclusion in TEAE tables, incomplete AE onset and end dates will be imputed as follows:

Missing onset dates (where UK and UKN indicate unknown or missing day and month respectively):

- UK-MMM-YYYY: If the month and year are different from the month and year of the first dose of study drug, assume 01-MMM-YYYY. If the month and year are the same as the first dose of study drug month and year, and the end date (after any imputation) is on or after the first dose of study drug, then assume the date of the first dose of study drug. If the month and year are the same as the first dose of study drug month, and year and the end date (after any imputation) is prior to the first dose of study drug, then assume the end date for the onset date.
- DD-UKN-YYYY/UK-UKN-YYYY: If the year is different from the year of first dose of study drug, assume 01-JAN-YYYY of the collected year. If the year is the same as the first dose of study drug year, and the end date (after any imputation) is on or after the first dose of study drug, then assume the date of the first dose of study drug. If the year is the same as the first dose of study drug, and the end date (after any imputation) is prior to the first dose of study drug, then assume the end date for the onset date.

Missing end dates (where UK and UKN indicate unknown or missing day and month respectively):

- UK-MMM-YYYY: Assume the last day of the month;
- DD-UKN-YYYY/UK-UKN-YYYY: Assume 31-DEC-YYYY.

For both ocular and non-ocular events, the following summaries will be produced:

- Overall summary of TEAEs
- TEAEs by SOC and PT
- Serious TEAEs
- Significant TEAEs by SOC and PT
- TEAEs Relationship by SOC and PT
- TEAEs Severity by SOC and PT
- TEAEs Leading to Treatment Discontinuation

If an eye (for eye level ocular summaries) or a subject (for non-ocular summaries and subject-level ocular summaries) reports the same preferred term multiple times, the eye or the subject will only be counted once for that preferred term. As with the preferred term, if an eye or a subject reports multiple adverse events within the same SOC, then the eye or the subject will only be counted once for that SOC.

The relationship of adverse events to study medication will be classified as not related and related. Any adverse event with a relationship of related or possibly related will be considered related. Any event with a relationship of not related or unlikely related will be considered not related. If a subject reports multiple occurrences of the same adverse event, only the most closely related (conservative) occurrence will be presented. Adverse events that have missing/unknown relationship will be presented in the summary table as “Related” but will be presented in the data listing with a missing/unknown relationship. Severity will be classified as mild, moderate and severe. If a subject reported multiple occurrences of the same adverse event, only the most severe will be presented. Adverse events that have missing/unknown severity will be presented on tables as “Severe” but will be presented in the data listing with a missing severity.

9.2. Subjects Reported Ocular Symptoms

Ocular symptoms reported at Visit 1, Visit 2 and any other unscheduled visit will be tabulated by treatment, visit and severity at eye level.

Possible symptoms are:

- Burning/Stinging
- Itchiness/Scratchiness
- Dryness
- Lens Awareness
- Grittiness/Foreign Body Sensation
- Redness
- Irritation/Discomfort
- Cloudy/Blurry/Hazy
- Variable Vision

- Other

9.3. Slit-lamp Findings

Any result of the slit-lamp assessment recorded at Visit 1, Visit 2 and any other unscheduled visit will also be tabulated at eye level by treatment, visit and grade. If no slit lamp finding is noted in one eye, this will be considered as having a Grade 0 and will be included in the table as well. Possible findings will be reported in the following order:

- Corneal Edema Grade
- Corneal Neovascularization Grade
- Corneal Staining Grade
- Corneal Staining Location
- Conjunctival Injection Grade
- Tarsal Abnormalities Grade
- Other Complications Grade

Corneal Neovascularization Location will only be presented in the listing of slit-lamp findings.

9.4. Reasons for Discontinuation

Primary reason for discontinuation collected at Visit 2 will be presented in Subject Disposition (see section 5).

9.5. Lens Information

The number of unplanned replacements, folded lenses and damaged lenses will be tabulated by treatment at eye level and subject level.

Type of damage will be summarized by treatment at eye and subject level and will include:

- Chip
- Discoloration
- Fracture
- Non-uniform Haze
- Non-wetting
- Petal Circular defect
- Scratch
- Tear
- Other

In addition, damage location will be tabulated by treatment at eye level and subject level, and will include:

- Peripheral
- Central
- Peripheral and Central

The reason for lens replacement and lens damage will be listed.

12.1. Schedule of Study Procedures

Visit Information	Visit 1 Screening, Baseline, Randomization, Lens Dispensing, Initial Clinical Assessments	Visit 2 1-Week Follow-up, Final Evaluation
Time Point	Day 1	Day 6-9
Estimated Visit Duration	2.0 hours	1.5 hours
Statement of Informed Consent	x	
Demographics	x	
Medical History/Concomitant Medications	x	x
Inclusion/Exclusion Criteria	x	
Habitual Contact Lens Information	x	
Compliance and Subject Reported Ocular Symptoms and Adverse Event Review	x	x
Entrance Snellen Distance Visual Acuity	x	x
Subjective Sphero-Cylindrical Refraction and visual acuities	x	x
Subjective Best Sphere Refraction and visual acuities	x	
Slit Lamp Classification Scale	x	x
Lens Assignment	x	
Lens Insertion & Settling	x	
Visual Acuity and Over Refraction	x	
Monocular logMAR Visual Performance (High Contrast, High Illumination)	x	x

Visit Information	Visit 1 Screening, Baseline, Randomization, Lens Dispensing, Initial Clinical Assessments	Visit 2 1-Week Follow-up, Final Evaluation
Time Point	Day 1	Day 6-9
Estimated Visit Duration	2.0 hours	1.5 hours
Lens Fit Assessment	x	x
Reported Average Wearing Time		x
CLUE Handling	x	x
Exit Snellen Distance Visual Acuity	x	x
Dispense Patient Instruction Guide	x	
Dispense Test Article	x	
Study Completion		x

12.2. Missing Data Pattern

Having 2 visits only and assuming the probability of observing the score at Visit 2 does not depend on the presence of the score at Visit 1, these are the possible patterns:

Group	Score V1	Score V2
1	X	X
2	X	.
3	.	X
4	.	.

Where ‘X’ represent a non-missing data and “.” represents a missing data.

These patterns apply to both left and right eye.

12.3. SAS Code for Sensitivity Analysis

The following SAS code will be used to generate the sensitivity analysis for the difference in visual acuity logMAR score (K-Lens versus Placebo), using a MI process for imputation of missing data.

Multiple imputation phase

```
proc mi data= yyyyyyy nimpute=20 seed=51343672 out=outmi ;
  class SITEID TREATMENT;
  var SITEID TREATMENT LOGMARV1_OD LOGMARV1_OS LOGMARV2_OD LOGMARV2_OS;
  fcs discrim(SITEID TREATMENT /classeffects=include) reg (LOGMARV1_OD LOGMARV1_OS LOGMARV2_OD
LOGMARV2_OS /details);
run;
```

In case the analysis of the missing data will show a monotone pattern, the same procedure will be executed with the MONOTONE statement.

```
proc mi data= yyyyyyy nimpute=20 seed=51343672 out=outmi ;
  class SITEID TREATMENT;
  var SITEID TREATMENT LOGMARV1_OD LOGMARV1_OS LOGMARV2_OD LOGMARV2_OS;
  monotone discrim (SITEID TREATMENT /classeffects=include) reg (LOGMARV1_OD LOGMARV1_OS
LOGMARV2_OD LOGMARV2_OS /details);
run;
```

where LOGMARV1_OD is the logmar score at the last visit, excluding unscheduled, prior to visit 2 for the right eye;
LOGMARV1_OS is the logmar score at the last visit, excluding unscheduled, prior to visit 2 for the left eye;
LOGMARV2_OD is the logmar score at visit 2 for the right eye;
LOGMARV2_OS is the logmar score at visit 2 for the left eye;
SITEID is site identifier within each study;
TREATMENT is the treatment variable (K-Lens/Placebo);

Analysis by imputation at each visit

```
proc glimmix data = outmi;
by _imputation_;
class treatment siteid subjid eye;
model logmar = treatment/ DDFM=KenwardRoger S;
random intercept /subject = siteid;
random eye / type=UN subject=subjid(siteid) group = treatment residual;
lsmeans treatment / diff=control('Placebo') cl;
covtest 'Common Variance' Homogeneity;
ods output ParameterEstimates=mixparms Covtests=mixcovtest CovParms=mixcovp diffss=diffs
lsmeans=lsmeans;
run;
```

If the hypothesis of homogeneity is accepted (chi-square test p-value > 0.05) the syntax “group = treatment” and the ‘covtest’ statement will be omitted from the final model.

The model will take into account using UN covariance matrix for each imputation dataset. In case the algorithm will not converge with the UN for a particular dataset, then the CS matrix will be used for such imputation dataset. This will be reviewed on a case by case basis.

Results combined for the inference at each timepoint and visit

```
proc mianalyze data=diffs;
modeleffects estimate;
stderr stderr;
ods output parameterestimates=parest;
run;

proc mianalyze data=lsmeans;
by treatment;
modeleffects estimate;
stderr stderr;
ods output parameterestimates=parest_lsmeans;
run;
```

where SITEID is site identifier within each study;
SUBJID is subject identifier;

TREATMENT is the treatment variable (K-Lens/Placebo);
LOGMAR is visual acuity logMAR score at Visit 2.

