2.3. Hypotheses

Primary Hypotheses

The K-Lens will be non-inferior to the Placebo lens with respect to monocular distance contact lens-corrected visual acuity. A non-inferiority margin of 0.1 logMAR (one line) units will be used.

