1.16	Lens Power Modification (if applicable)	
Adjust the lens power if the subject's best sphere over-refraction is not plano.
 
One power modification is allowed. If the subject's best sphere over-refraction is not plano, the subject will have to return no sooner than the following day, since subjects are not allowed to wear more than one lens per eye per day. When a subject returns for another lens, new baseline information must be recorded (starting with step 1.7), and then proceed per protocol through the remaining Visit 1 steps.
	
1.17	Subject Reported Ocular Symptoms	Subjects will respond to a verbal open-ended symptoms questionnaire.	
1.18	Subjective Lens Fit Assessment	
Evaluate overall lens fit acceptance (acceptable or unacceptable) based on centration, movement and other fitting characteristics.
 
An unacceptable fit is deemed by one of the following criteria:
 
 • limbal exposure at primary gaze or with extreme eye movement; • edge lift; • excessive movement in primary and up gaze; or • insufficient movement in all three of the following conditions: primary gaze, up gaze, and push up test. 
Note: if lens fit is unacceptable subject will be discontinued from the study.
	
1.19	Distance ETDRS LogMAR Visual Acuity	
Perform monocular distance ETDRS LogMAR visual acuity test at a 4-meter distance over the test eye only under the following condition:
 
 • bright illumination (e.g., >400 lux), high luminance, with high contrast charts (HLHC); 
The Precision Vision 4-meter high contrast ETDRS charts (Chart 1 and Chart 2) will be used.
 
One measurement will be recorded per eye.
	

1.20	Exit Snellen VA	Record subjects' distance visual acuity, OD, OS and OU to the nearest letter. [REDACTED]	
1.21	Continuance	For the subject to continue in the study, they must meet all three of the following criteria: 
 • Visual acuity is 20/30 or better OD and OS • The lens fit is acceptable OD and OS • Investigator approval. If the Investigator does not approve the dispensing of the first study lens, then the study is terminated for that subject. 	

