14.2. Sample Size Justification

The study is designed to evaluate the clinical performance of K-Lens produced on the new JJVC manufacturing line in Limerick, Ireland with the primary objective to show that the K-Lens is non-inferior to the Placebo lens with respect to best-corrected distance visual acuity. The plan is to enroll 132 eligible subjects with a target completion of 120 subjects (80 subjects in K-Lens and 40 subjects in Placebo).

The sample size of 120 subjects is considered sufficiently large to test for non-inferiority with a minimum statistical power of 85% and two-sided type I error of 0.05. Assuming a perfect correlation between left eye visual acuity and the right eye visual acuity (worst case scenario), the total sample size (n) required to achieve 85% power with two-sided type I error of 0.05 was calculated for different scenarios of mean difference (Δ = K-Lens – Placebo) and common standard deviation (σ) in the two arms. The results are summarized in the Table below:

Table 4: Sample size for different scenarios of mean Δ and σ

Δ	σ	n
0	0.05	15
0	0.01	45
0.04	0.05	33
0.04	0.1	117

The sample size calculation was conducted using the PROC POWER Procedure (SAS/STAT 14.1, SAS Institute, 2015) for two-sample means with allocation weight of 2:1.

Justification of Non-inferiority margin:

The non-inferiority margin of one line loss on best-corrected distance visual acuity was considered based on the work done by Jane E. Lovie-Kitchin and Brian Brown on evaluating the repeatability and intercorrelations of five standard vision tests in subjects with normal vision. The authors concluded that one line change is, on average, a useful criterion to adopt on clinical decision making²³.

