4.4. Handling of Missing Data

For the primary endpoint (visual acuity logMAR score), a sensitivity analysis will be conducted to explore the impact of missing data. This sensitivity analysis rely on an assumption that the missing data are missing at random (MAR) i.e., that the probability that an observation is missing can depend on observed data but is unrelated to the data not observed.

The sensitivity analysis will be based on multiple imputation analysis explained in section 8. Observed missing data are detailed in Appendix 12.2: Missing data pattern.

5. Subject Disposition

A disposition of subjects including the number and percentage of subjects enrolled, subjects adhering to protocol (PP population), subjects treated (safety population), subjects completed, subjects discontinued from the study and subjects enrolled but not dispensed will be summarized by the 2 treatment groups. In addition subjects enrolled but not randomized will be also included (where relevant).

Subjects will be allocated to one of the three mutually exclusive groups:

- Completed: Subjects are considered to have completed the study if (1) they are eligible, (2) not discontinued, (3) they have completed all visits including the final visit (Visit 2).
- Discontinued: Subjects are considered to have discontinued from the study if (1) test article administered and (2) discontinued because of one of the following reasons:
 - Adverse Event;
 - Unsatisfactory Visual Response due to test article;
 - Unsatisfactory Lens Fitting due to test article;
 - Lens Discomfort;
 - Lens Handling Difficulties;
 - Withdrew Consent during study;
 - Lost to Follow Up;
 - Subject no longer meets Eligibility Criteria;
 - Subject Withdrawn by PI due to non-compliance to protocol;

- Test Article No Longer Available;
 - Other.
- Enrolled but Not Dispensed: Subjects are considered Enrolled but Not Dispensed if they provide informed consent but (1) failed to satisfy the eligibility criteria (inclusion/exclusion criteria) or (2) were randomized but test article was not administered for any reason.

Total Enrolled = Completed + Discontinued + Enrolled Not Dispensed.

The reasons for study discontinuation and study withdrawal will also be summarized.

All percentages will be based on the number of total enrolled subjects.

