7.2.1. Treatment Compliance and Extent of Exposure

The treatment compliance will be assessed at follow-up visit (Visit 2) at eye level. The following information will be summarized by treatment at subject level for both subjects in PP and safety population:

- Number of days wearing the lens
- Wearing time on Visit 2 (hours)

The number of subjects not wearing the lens at Visit 2 will be tabulated at subject level by treatment for subjects in safety population.

No modification to the daily treatment regimen is planned.

8. Efficacy Analysis

All the efficacy analyses will be conducted on PP population comparing K-Lens against Placebo.

As supportive analysis, the efficacy analysis will be repeated on the mITT population regardless of missing data.

In addition, a sensitivity analysis will be conducted on the primary endpoint using the mITT population to assess the impact of missing data using a multiple imputation (MI) process. Missing values for visual acuity logMAR score will be imputed from a regression model with treatment group, analysis site and logMAR score at Visit 1 and Visit 2 as covariates. Twenty imputations²⁸ will be performed using SAS PROC MI with the Fully Conditional Specification (FCS) option to take into account non-monotone missing data pattern (see Appendix 12.2: Missing data pattern). In case the pattern of missing data will be monotone, the procedure will use an imputation method for data sets with monotone missingness. The adjusted means difference between treatments and its standard error will be displayed with corresponding two-sided 95% CI and non-inferiority flag calculated using the SAS MIANALYZE procedure to combine the results of the analyses performed by imputation. See Appendix 12.3 for the SAS PROC MI, PROC MIXED and PROC MIANALYZE specifications.

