The log-likelihood ratio test will be used to test for the homogeneity between the residual covariance structures across treatment groups. The Kenward and Roger method will be used to calculate the denominator degree of freedom.²⁵

The null and alternative hypotheses for non-inferiority of K-Lens relative to Placebo are as follows:

$$H_0: \Delta \geq 0.1$$
$$H_A: \Delta < 0.1$$

where Δ is the mean difference in visual acuity between K-Lens and Placebo (K-Lens minus Placebo). The non-inferiority test will be based on the least-square mean difference (K-Lens minus Placebo) and corresponding 95% confidence interval calculated using the final selected model. The upper bound of the 95% confidence interval will be compared to the non-inferiority margin of 0.1 LogMAR. If the upper bound is less than 0.1, K-Lens will be considered non-inferior to Placebo with respect to visual acuity.

The following code will be used to run the mixed model.

```
proc glimmix data = dataset plots=ResidualPanel;
class treatment siteid subjid eye;
model logmar = treatment/ DDFM=KenwardRoger S;
random intercept /subject = siteid;
random eye / type=matrix_cov subject=subjid(siteid) group = treatment
residual;
lsmeans treatment / diff=control('Placebo') cl;
covtest 'Common Variance' Homogeneity;
ods output ParameterEstimates=parms Covtests=mixcovtest
CovParms=mixcovp diffss=diffs lsmeans=lsmeans;run;
```

Where:

- “Treatment” is the treatment group variable (K-Lens/Placebo);
- “Siteid” is the investigator site identifier;
- “Eye” is the variable to identify which eye the observation belongs to (left/right);
- “Subjid” is the subject identifier;
- “Matrix_cov” is the covariance structure (UN/CS) between the left eye visual acuity and right eye visual acuity.

If the hypothesis of homogeneity is accepted (chi-square test p-value > 0.05) the syntax “group = treatment” and the ‘covtest’ statement will be omitted from the final model.

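### The imputation sensitivity analysis omits the Visit 1 exit Snellen acuity that apparently decides who continues, so subjects stopped for poor acuity are imputed slightly too well

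*SAP*

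**What the plan says.** SAP section 8 plans a multiple-imputation sensitivity analysis of the primary endpoint in the mITT population. Missing scores are "imputed from a regression model with treatment group, analysis site and logMAR score at Visit 1 and Visit 2 as covariates". Both PROC MI calls in SAP 12.3 (FCS and MONOTONE) carry the same list: "var SITEID TREATMENT LOGMARV1_OD LOGMARV1_OS LOGMARV2_OD LOGMARV2_OS". No Snellen variable appears in the text or the code.

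SAP 4.4 rests this analysis on missing at random, meaning that "the probability that an observation is missing can depend on observed data but is unrelated to the data not observed".

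In Protocol 7.2, Visit 1, step 1.19 records ETDRS logMAR for each eye. Step 1.20 records exit Snellen "distance visual acuity, OD, OS and OU to the nearest letter". Step 1.21 then sets three conditions for continuing: acceptable fit, investigator approval, and "Visual acuity is 20/30 or better OD and OS".

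The margin is stated in Protocol 2.3: "A non-inferiority margin of 0.1 logMAR (one line) units will be used". The decision rule is in SAP 8.1: "The upper bound of the 95% confidence interval will be compared to the non-inferiority margin of 0.1 LogMAR". Higher logMAR is worse.

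**The concern.** A subject who fails the acuity condition at step 1.21 is not dispensed lenses and has no Visit 2 logMAR. That subject has already worn a study lens, so belongs to mITT (SAP 4.3.3), but has not completed all visits, so is outside the per-protocol set (SAP 4.3.4). The unimputed mITT analysis has no Visit 2 value for this subject. The imputation is therefore the only planned analysis that returns such subjects to the comparison.

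If the condition is judged on the step 1.20 Snellen reading, the imputation leaves out the variable that decides this missingness. Among subjects with the same step 1.19 logMAR, those who failed on Snellen have worse expected acuity than those who passed. The regression is fitted to those who passed, so it predicts too well for those who failed. If K-Lens gives poorer acuity, more K-Lens subjects fail, and the error pulls the K-Lens minus Placebo difference down, towards non-inferiority. That is the case this analysis exists to check.

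**Working it through.** **The plan's own figure.** Inputs: margin 0.1, one-sided 0.025, 85% power, 2:1 allocation (Protocol 14.2: "with a minimum statistical power of 85% and two-sided type I error of 0.05"). Normal approximation for Δ = 0.04, σ = 0.1: n = (1.960 + 1.036)² × 0.1² × (3/2 + 3) / (0.1 − 0.04)² ≈ 112, or 114 as a multiple of three. The exact noncentral-t calculation gives 117, as printed. All four rows reproduce (15, 45, 33, 117) if the σ printed as 0.01 in the second row is read as 0.1; that is a separate point. The planned loss is (132 − 120)/132 = 9.1%.

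**Assumptions for the simulation.** The documents give no Snellen/logMAR correlation and no failure rate, so these are assumed:
- 88:44 subjects, two eyes each, between-eye correlation 0.8.
- SD 0.05 or 0.1; Placebo mean 0 or −0.1 logMAR; reliability of a single reading 0.5 to 0.9.
- None or half of the visit error shared between Snellen and Visit 1 logMAR.
- A subject is stopped if Snellen exceeds log10(30/20) = 0.176 in either eye.
- Twenty regression imputations with Rubin's rules; analysis of the subject's two-eye mean; no site effects and no other dropout.

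**True difference 0.10, 4,000 runs per row.** Monte Carlo error at 2.5% is √(0.025 × 0.975/4000) = 0.25 percentage points.

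| Setting | Stopped, K-Lens / Placebo | Imputed too well by | Estimate: full data → SAP model | False flag: SAP model | False flag: Snellen added | False flag: completers |
|---|---|---|---|---|---|---|
| A: SD 0.1, mean 0, reliability 0.5 | 35.6% / 7.2% | 0.0343 | 0.0999 → 0.0910 | 8.9% | 2.8% | 27.3% |
| B: SD 0.1, mean 0, reliability 0.8 | 32.7% / 6.6% | 0.0218 | 0.1005 → 0.0954 | 5.1% | 2.2% | 47.7% |
| C: as B, half the error shared | 32.6% / 6.5% | 0.0113 | 0.1002 → 0.0975 | 3.6% | 2.2% | 49.0% |
| D: as B, Placebo mean −0.1 | 6.6% / 0.5% | 0.0217 | 0.1001 → 0.0989 | 3.2% | 2.6% | 8.6% |
| E: SD 0.05, mean 0, reliability 0.8 | 10.4% / 0.0% | 0.0104 | 0.1000 → 0.0990 | 3.6% | 2.5% | 15.6% |

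**Hand check.** Shift ≈ (difference in stopped proportions) × (amount imputed too well):
- A: 0.284 × 0.0343 = 0.0097 (simulated 0.0089)
- B: 0.261 × 0.0218 = 0.0057 (0.0051)
- C: 0.261 × 0.0113 = 0.0029 (0.0027)
- D: 0.061 × 0.0217 = 0.0013 (0.0012)
- E: 0.104 × 0.0104 = 0.0011 (0.0010)

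**Against the planned loss.** Overall proportion stopped at the gate is (88 × K-Lens + 44 × Placebo)/132: about 26%, 24%, 24%, 4.6% and 6.9% for A to E. Only D and E fit inside the 9.1% allowed for all causes; there the flag rate is 3.2% and 3.6%. One shorter run (SD 0.05, reliability 0.5, 11.7% of K-Lens stopped) gave 5.2%, but its full-data rate was already 3.0%.

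**Other true differences.** At 0 the error cancels between arms (within 0.0003). At 0.04 the estimate is low by about 0.0001 to 0.003. At −0.04 it moves from −0.0399 to −0.0391, so the pull is towards zero. Across all settings stopped subjects are imputed 0.005 to 0.045 too well; the top value comes from a setting with about 0.1% stopped and rests on very few subjects. If Snellen equals Visit 1 logMAR exactly, the error disappears (estimate 0.1001, flag 2.5%).

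**A second simulation.** With six sites, inter-eye correlation 0.6, SD 0.08 to 0.10 and Snellen noise 0.05 to 0.07, a true 0.10 was estimated as 0.0935 to 0.098, with a flag rate of 4.2% to 6.0%. Adding Snellen gave 0.100 and 2.4% to 2.8%. Those settings imply about 16% to 42% of K-Lens subjects stopped.

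**The case against.** Several points on the other side stand.
- **Chart not named.** Step 1.21 gives no chart. Acuity is also recorded at steps 1.15 and 1.19, and part of step 1.20 is blacked out. If sites judged on step 1.19 logMAR, the point falls away. Snellen is the likelier reading: 20/30 is Snellen notation, step 1.20 comes directly before, and inclusion criterion 7 labels its own 20/30 limit as Snellen.
- **One route among many.** Protocol 8.2 and SAP section 5 list adverse events, discomfort, loss to follow-up and others. Subjects stopped for fit at step 1.18 may lack even Visit 1 logMAR. Nothing shows that acuity failure will be the main cause of missing data.
- **High failure rates needed.** The larger effects mostly need far more failures than the 9.1% planned loss. The simulations also leave out the 20/30 eligibility screen and the step 1.16 power change. Applying a 20/30 screen in one setting moved the estimate from 0.094 to 0.0954, with little change in the flag rate (5.5% to 5.3%).
- **Small shift.** The largest, about 0.009 logMAR, is under half a letter at 0.1/5 = 0.02 per letter. Visit 1 logMAR is a good proxy, so the planned imputation already removes most of the completers' error.

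These points limit the weight. They do not show that leaving out a recorded predictor of missingness is harmless.

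**Conclusion.** The point holds as an inexpensive improvement to a sensitivity analysis. If the step 1.21 condition is judged on Snellen, the imputation model is too optimistic for subjects stopped there. The direction does not depend on the assumed noise, provided Snellen and Visit 1 logMAR are not identical; the size does. The error is negligible when failures are few. It reaches several thousandths of a logMAR unit only when K-Lens is truly worse by about the margin and failures are common and unequal.

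Two stronger readings are tempting and not supported. A reader might infer that the plan breaks its own missing-at-random assumption. It does not: exit Snellen is recorded, so missingness driven by it satisfies SAP 4.4 as worded. What fails is missing at random given the variables in the imputation. A reader might also infer that the trial would falsely conclude non-inferiority at the rates above. Those rates concern the flag from the sensitivity analysis. The trial's conclusion rests on the per-protocol analysis, which this model does not touch. That analysis drops the stopped subjects, and in the same simulations the completer analysis erred further in the same direction, which is a reason to make this check sound.

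**What to change.** In SAP section 8, add each eye's Visit 1 exit Snellen acuity through the study lens (step 1.20) to the imputation covariates. In SAP 12.3, add the two variables (OD and OS) to the VAR and REG lists of both PROC MI calls, after the Visit 1 logMAR variables and before the Visit 2 ones. The order matters for the MONOTONE call, which imputes each variable from those listed before it. Take the reading from the same, last Visit 1 evaluation that supplies the Visit 1 logMAR.

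The visible documents give no conversion from Snellen to the nearest letter into logMAR, so the SAP should state one. It should also state that the step 1.21 condition is taken to be judged on the step 1.20 reading, once the sponsor has confirmed this.

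Cost: two variables already collected, a short SAP addition including the conversion rule, and a standard error about 1% to 5% larger in simulation. No new data, no change to clinical procedures, and no change to the primary analysis.
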